At the end of the individual N-of-1 trials, statistical analyses will be conducted to compare the outcomes of anti-stress interventions vs. no treatment. In a first step, the data will be presented descriptively by producing line plots of the N-of-1 trials. In a second step, Bayesian linear regression models with normally distributed errors will be used to compare the average ratings of same-day stress levels and the level of stress expected for the following day (the two primary outcomes) during periods of anti-stress interventions to those with no treatment using R's "brms" package. Non-informative priors will be used for all parameters since no prior information was available before the study to provide a reasonable effect estimate of anti-stress interventions in reducing daily stress levels. Given the longitudinal nature of our data, we will employ a first-order autoregressive (AR1) error structure to recognize that measurements taken at adjacent times have a higher dependence compared to those taken at more distant intervals. Algorithm convergence will be assessed by the parameters R^2 , Bulk_ESS and Tail_ESS and assumptions of the models will be checked. Separate analyses will be performed for each individual to compare the average response to treatment. Based on this model, estimates of the posterior distribution of the average anti-stress intervention effect on the primary outcomes (daily stress and expected level of stress for the following day) at the individual level will be obtained. We will report the mean posterior distribution and the 95% credible interval. Additionally, we will report the probability to achieve a clinically relevant intervention effect which is defined as a reduction of 0.5 points of the stress scale (range 1 to 10).

Analyses of the Aggregated N-of-1 Trials

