In order to estimate population-level intervention effects, a Bayesian multi-level linear regression model will be utilized to evaluate the efficacy of anti-stress interventions compared to no treatment on the primary outcomes, the same-day stress levels and the level of stress expected for the following day, at the population level. This will be done separately for those participants that chose the mindfulness intervention and the box breathing exercise. Bayesian multi-level mixed models will be employed to estimate the posterior distribution of the population-level average treatment effect. For the aggregated analysis, non-informative priors will be used for all parameters since no prior information was available to reasonably estimate the effect of anti-stress interventions on reducing daily stress levels. In line with the analyses of the individual N-of-1 trials described above, we will include a first-order autoregressive (AR1) error structure to account for the higher dependence of measurements taken at adjacent times compared to those taken further apart. Similar to the individual-level model previously described, estimates of the posterior distribution of the average anti-stress intervention effect on the population level in reducing daily stress levels will be obtained. The posterior distribution of the mean difference between the outcomes of anti-stress interventions and no treatment will be derived from the aggregated Bayesian model. Similarly to the individual-level analyses, we will report the mean of the posterior probability distribution, the 95% credible interval, and the probability to achieve a clinically relevant reduction in stress levels of 0.5 points.

As a secondary analysis, we will perform a joint analysis of both interventions to estimate the effect of the availability of an anti-stress intervention among the participants who

chose the respective intervention on the daily stress level and the level of stress expected for the following day. Secondary outcomes will be modeled and reported similarly.

Effect Measure Modifiers

The impact of baseline effect measure modifiers, which were recorded before randomization to the treatment schedule, namely sex, the baseline stress level (Cohen's PSS) and the place of work (hospital vs. outpatient clinic), will be assessed exploratively in stratified subgroup analyses and by incorporating these variables as interaction terms in the Bayesian models.

Additional Analyses

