As additional analyses, frequentist linear mixed regression models are calculated using the same model-specifications as described for the Bayesian models above. Additionally, a per-protocol analysis will be performed (see below).

Protocol deviations

Protocol adherence will be assessed by comparing the response to the daily question about the performance of the intervention/exercise matches with the current period (intervention vs. control). Additionally, if less than $n=16$ PROs are documented, the participant will be excluded from the per-protocol analysis which will be performed as part of the sensitivity analyses.

Missing Data

Regarding the data obtained from the StudyU App, we will conduct complete-case analyses, assuming that the missing values are completely random. If participants did not complete the N-of-1 trial, we will analyze all the available data. In the psychological questionnaires, the final scores are calculated as the mean of all answered items. If more than 50% of the items remain unanswered, a score is not calculated.

Analysis Populations

Intention-To-Treat (ITT)

The main analyses utilize the ITT population, which includes all randomized participants, irrespective of whether they completed the entire study period and received the assigned intervention. Data from participants who did not complete the N-of-1 trial will be included in the analyses up to that point.

Per-Protocol (PP)

As an additional analysis, a per-protocol analysis will be performed including only participants with at least $n=16$ documented PROs and a protocol adherence of 85% or higher.

Safety and Adverse Events

Adverse events were not recorded during the study period but are assessed as part of the follow-up questionnaire and will be reported descriptively.

Statistical Software

Analyses will be conducted using R version 4.4.1.

Difference to trial protocol

--

References

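### Does the aggregated model need its participant-level terms and the prior on their spread written out before the population interval can be trusted?

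*SAP*

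**What the plan says.** In the SAP, Analyses of the Aggregated N-of-1 Trials, "a Bayesian multi-level linear regression model will be utilized to evaluate the efficacy of anti-stress interventions compared to no treatment on the primary outcomes". The next lines split the fit by chosen exercise ("This will be done separately for those participants that chose the mindfulness intervention and the box breathing exercise") and name the target: "Bayesian multi-level mixed models will be employed to estimate the posterior distribution of the population-level average treatment effect". On priors, "non-informative priors will be used for all parameters since no prior information was available to reasonably estimate the effect of anti-stress interventions". On residual dependence, "we will include a first-order autoregressive (AR1) error structure to account for the higher dependence of measurements taken at adjacent times". The reported quantities are the posterior mean, the 95% credible interval and the probability of a reduction of 0.5 points.

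Three neighbouring statements bear on how this is read:

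- Analyses of Individual N-of-1 Trials: "Separate analyses will be performed for each individual to compare the average response to treatment".
- Effect Measure Modifiers: interactions with sex, baseline stress and place of work are to be explored.
- Additional Analyses: "frequentist linear mixed regression models are calculated using the same model-specifications as described for the Bayesian models above".

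No section lists the random terms of the aggregated model or names a distribution for a between-person SD.

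**The concern.** Two models satisfy the literal text. One has a random intercept and a single treatment effect shared by everyone. The other adds a treatment effect that varies by participant. Their posterior means may be close, but their intervals are not if people respond differently. The common-effect interval leaves out the between-person variance of the effect. It is therefore too short for a population mean, and the probability of a 0.5-point mean reduction becomes too extreme in either direction. The frequentist models take over the same specification, so they would not reveal the difference.

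The prior rule adds a second gap. Its stated reason concerns the treatment effect only. For a between-person SD, non-informative has no unique meaning: flat on the SD and flat on the variance are different priors. With few participants per exercise they give different widths. If both choices stayed open until the data were seen, the more favourable interval could be picked.

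**Working it through.** **Inputs.** The SAP states no number of participants, days, SD or between-person SD, so there is no figure of its own to reproduce. From the SAP come the 0.5-point threshold on a 1 to 10 scale and the minimum of 16 documented PROs for the per-protocol set. Everything else is assumed: 28 days in alternating 7-day periods, residual SD 1.5, AR(1) coefficient 0.3, n = 10 or 30 per exercise, estimated mean reduction 0.7, and between-person SD of the effect τ = 0.3, 0.5 or 0.8.

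**Step 1, precision of one person's effect.** Generalised least squares with an intercept and a treatment indicator under the AR(1) covariance gives a standard error s = 0.679. For 16 days in 4-day periods s = 0.831. For 56 days in 7-day periods s = 0.475.

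**Step 2, the two standard errors.** Common effect: s/√n. Random effect: √(s² + τ²)/√n. The ratio is R = √(s² + τ²)/s, and the nominal 95% common-effect interval covers the population mean with probability 2Φ(1.96/R) − 1.

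**Step 3, probability of a mean reduction of at least 0.5.** With an estimated reduction of 0.7 and a normal approximation this is Φ(0.2/SE). For n = 30 the common-effect SE is 0.679/√30 = 0.124, which gives Φ(1.61) = 0.95. The last column below is the same quantity with the random-effect SE.

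| τ | R | Coverage of common-effect interval | Random-effect SE (n=30) | Probability, random effect |
|---|---|---|---|---|
| 0.3 | 1.09 | 92.7% | 0.136 | 0.93 |
| 0.5 | 1.24 | 88.6% | 0.154 | 0.90 |
| 0.8 | 1.54 | 79.5% | 0.192 | 0.85 |

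Across 16 to 56 days, coverage runs from 91% to 82% at τ = 0.5 and from 84% to 68% at τ = 0.8.

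**Step 4, check with fitted variances.** In REML simulations standing in for the flat-prior fits (800 trials per setting, Monte Carlo error about 0.5 to 1.4 points), the common-effect interval covered 93%, 87% and 82% at τ = 0.3, 0.5 and 0.8 with n = 30. With n = 10 it covered 92%, 91% and 82%. With a random treatment effect coverage was 94 to 98%. A separate simulation (n = 20, 200 trials per setting, intercept SD 1) gave 88% against 93% at τ = 0.5, and 70% against 91% at τ = 1.0. At τ = 0 both models covered about 95 to 96%. For the average over the enrolled participants themselves, the common-effect interval covered 95 to 96%.

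**Step 5, prior on τ.** The check uses a two-stage normal model with known s = 0.679, a sample variance of effects equal to s² + 0.5², a flat prior on the mean and grid integration over τ up to 50. The 95% interval widths are:

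- n = 30: 0.62 (flat SD) and 0.66 (flat variance), about 6% apart.
- n = 10: 1.22 and 1.45, about 19% apart.

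A flat prior on log τ is not a usable comparator. Its posterior is improper, and its width depends on where the grid is cut: at n = 10 it is 0.94 with the cut at 0.001 and 1.03 with the cut at 0.05.

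**The case for a change.** The strongest case for a change is that a model formula is core SAP content, that the two named outputs at stake belong to both primary outcomes, and that the plan itself expects people to respond differently. On that view the random treatment effect is the term that most needs stating, and a line for the model and a line for the prior would cost almost nothing.

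Part of this stands. The terms are not listed, the literal text does not exclude a common effect, and the direction of the error is as described whenever τ exceeds zero.

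The size argument is weaker. The largest contrast, 0.95 against 0.85, needs τ = 0.8. That exceeds both the SAP's 0.5-point threshold and the assumed mean reduction of 0.7, and it implies that Φ(−0.7/0.8), about 19% of participants, are made worse. Nothing in the SAP supports such a spread. The fitted models also often lose less coverage than the known-variance formula: 82% rather than 79.5% at τ = 0.8, and 91% rather than 88.6% at n = 10 and τ = 0.5. The low end of the 16 to 56 day range may therefore be pessimistic.

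The prior argument rests on small groups. Splitting by exercise makes each group smaller than the total, but the SAP gives no n, and at 30 per group the choice between the two usable priors hardly matters.

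**Conclusion.** No change to the plan is needed. The section states no wrong rule and contradicts nothing. It leaves unwritten a detail that its own wording points to. Multi-level and mixed rule out full pooling. A population average effect, reported beside individually estimated effects and planned interactions, points to effects that vary by person. An analyst building the model from this text would ordinarily include a participant-level intercept and treatment effect, with AR(1) errors within each participant. Writing out the formula would record that reading rather than alter the analysis.

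For the concern to do harm, the analyst must fit a common effect and effects must vary materially. Under the assumptions above, the cost is then about 2 points of coverage at τ = 0.3 and 6 to 8 points at τ = 0.5 (n = 30 simulation and formula). It is larger only for spreads that the SAP gives no reason to expect. If effects hardly vary, the two fits nearly agree. The individual-level estimates, which the SAP also treats as primary, are untouched. On the prior, no particular choice is shown to be needed, and the sizeable difference appears only at an assumed 10 participants per group. All figures depend on assumed sample size, trial length, residual SD, autocorrelation and τ.

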Analysis Principles for Final Analyses

The primary analyses will provide individual-level and population-level estimates of the average efficacy of anti-stress interventions in reducing same-day stress levels and reducing the level of expected stress on the following day (the two primary outcomes) based on the series of N-of-1 trials. Both individual-level and population-level analyses will be based on the intention-to-treat population. That is, the individual-level analyses will include all observed data points and the pre-specified intervention schedule, independently of whether the intervention was performed. The population-level analyses will include all participants of the study population that started a trial and their pre-specified study design and intervention schedule, and all their recorded data, independently of whether the intervention was performed as pre-specified and independently if or when the study participants dropped out of the study. As a result of this, all analyses will evaluate the effect of the availability of the anti-stress interventions which mirrors the effect of the intervention if there is high adherence to the pre-defined intervention schedule.

Analyses of Individual N-of-1 Trials

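### Does one pooled 85% adherence threshold make the per-protocol set too lax about missed exercises?

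*SAP*

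**What the plan says.** Under "Protocol deviations", the SAP assesses adherence by "comparing the response to the daily question about the performance of the intervention/exercise matches with the current period (intervention vs. control"). The same section adds that with fewer than 16 "PROs are documented, the participant will be excluded from the per-protocol analysis", and it places that analysis among the sensitivity analyses. Under "Analysis Populations", the per-protocol paragraph repeats the minimum of 16 and adds the second condition: "documented PROs and a protocol adherence of 85% or higher". Neither figure is given by condition, and the denominator of the 85% is not stated.

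Two other sections bear on the point. *Analyses of Individual N-of-1 Trials* sets the contrast: outcomes "during periods of anti-stress interventions to those with no treatment". *Analysis Principles for Final Analyses* says that the intention-to-treat analyses estimate the effect of having the intervention available, which "mirrors the effect of the intervention if there is high adherence to the pre-defined intervention schedule".

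**The concern.** The comparator is no treatment, so a control day is adherent when nothing is done. That is likely to be easier than doing an exercise. When both kinds of day feed one percentage, easy matches on control days can make up for missed exercises, and a participant labelled 85% adherent may have skipped a quarter or more of them. The minimum of 16 PROs is pooled too, so it does not secure any number of documented intervention days.

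The per-protocol analysis is the only planned analysis restricted by adherence. The SAP makes the reading of its main result as an intervention effect depend on high adherence. A loose per-protocol set would pull its estimate towards the intention-to-treat effect, and agreement between the two could be taken as more reassurance than it gives.

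**Working it through.** The SAP derives no figure here; 85% and 16 are chosen thresholds, so there is nothing to reproduce. Two things can be checked: the worst case the rule admits, and what it does on average.

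**Worst case**

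Inputs from the SAP: threshold 85%; minimum 16 PROs. Assumed: *n* days, half of them intervention days.

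- Allowed mismatches: *m* = *n* − ceil(0.85 *n*).
- Floor, if every mismatch is a missed exercise: (*n*/2 − *m*) / (*n*/2).

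| *n* | matches needed | *m* | floor, pooled rule | floor, 85% per condition |
|---|---|---|---|---|
| 16 | 14 | 2 | 6/8 = 75% | 7/8 = 87.5% |
| 18 | 16 | 2 | 7/9 = 77.8% | 8/9 = 88.9% |
| 20 | 17 | 3 | 7/10 = 70% | 9/10 = 90% |
| 28 | 24 | 4 | 10/14 = 71.4% | 12/14 = 85.7% |
| 42 | 36 | 6 | 15/21 = 71.4% | 18/21 = 85.7% |

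For even *n* from 16 to 60 the pooled floor lies between 70.0% and 77.8%. For large *n* it tends to 1 − 0.15/0.5 = 70%.

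If the denominator is documented days and only a share *p* of them are intervention days, the large-*n* floor is max(0, 1 − 0.15/*p*): 62.5% at *p* = 0.4 and 50% at *p* = 0.3. Such floors need records that lean clearly towards control days. The SAP's "Missing Data" section assumes completely random missingness, under which no such lean is expected; dropout could produce it in individual participants.

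**Average effect**

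The per-protocol estimate averages over everyone in the set, so the floor does not describe it. An illustrative simulation of 400,000 participants shows the average. All its inputs are assumptions: 14 days per condition, all documented; exercise uptake varying between participants as a Beta distribution with mean 0.80 and concentration 5; a control-day match probability of 0.98.

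| | pooled 85% | 85% per condition |
|---|---|---|
| participants kept | 74% | 55% |
| mean uptake on intervention days | 89.3% | 93.8% |
| exercising on control days | 1.7% | 1.9% |
| share of the set below 85% uptake | 25% | 0% |

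Suppose the exercise lowers stress by 0.5 points on days it is done (the SAP's clinically relevant reduction) and has no effect on other days. The average contrast is then 0.5 × (uptake on intervention days − exercising on control days):

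- intention-to-treat: 0.5 × (0.80 − 0.02) = 0.39;
- pooled per-protocol: 0.5 × (0.893 − 0.017) = 0.438;
- per-protocol with a threshold per condition: 0.5 × (0.938 − 0.019) = 0.460.

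Splitting the threshold therefore gains 0.460 − 0.438 ≈ 0.02 points and drops 74 − 55 = 19 percentage points of participants. Only 9.6% of the pooled set sits at the floor of 10/14.

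**Range**

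Fully crossing mean uptake 0.7–0.9, concentration 4–8, 8, 14 or 21 days per condition and control match 0.95–1.0 gives:

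- gain in the estimate from splitting: 0.01–0.04 points;
- share of participants lost by splitting: about 9–30 percentage points;
- participants kept: 46–93% under the pooled rule, 26–80% under the split rule.

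**The case for a change.** The strongest case for a change is that the pooled figure does not bound the quantity of most interest, uptake on intervention days. In the base simulation a quarter of the pooled set falls below 85% on those days, and over the crossed range about 7% to 54% does. A reader who takes the label at face value would be misled about those participants. The remedy would take one or two sentences and could keep control-day adherence as a criterion of its own. The unstated denominator also decides who enters the set.

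The description stands: the rule bounds overall agreement with the schedule and no more. What does not follow is that the rule is wrong. Exercising in a control period is a deviation as well, and the SAP speaks of adherence to a pre-defined schedule, which contains both kinds of period. A pooled share of schedule-matched days measures that. Nor does the SAP assign the per-protocol analysis the task of testing whether adherence was high; it calls it an additional analysis.

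The split rule also has a cost in participants. The SAP's main population-level models are fitted separately for mindfulness and box breathing, so each per-protocol set is already a subset of a subset. On the denominator, the two readings coincide when every day is documented. Otherwise an analyst has to choose one and say so, which is ordinary practice for a sensitivity population.

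**Conclusion.** No change follows. The rule is looser on intervention days than its 85% suggests, with a worst case of about 70–78% under an even split, but it contradicts nothing in the SAP and fits the SAP's own notion of adherence. On average it costs about 0.02 points of a 0.5-point effect (0.01–0.04 over the assumed range), on a scale from 1 to 10. Tightening it would remove about 19 percentage points of participants in the base case and about 9–30 over the range. That is a fair trade-off in a sensitivity analysis, and the primary intention-to-treat results do not depend on it.

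The denominator, and a display of adherence on intervention and control days within the set, are details that a careful analyst supplies when reporting.

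The sizes rest on an even split of days, full documentation, no effect of a missed exercise, and the assumed spread of uptake; the SAP gives none of these. If the actual records leaned heavily towards control days, individual floors would be lower, and adherence reported by condition would show it.

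### Does the 85% adherence cut-off leave the per-protocol set open because the SAP names no denominator?

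*SAP*

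**What the plan says.** Under Analysis Populations, Per-Protocol (PP), the SAP restricts an additional analysis to participants with at least 16 "documented PROs and a protocol adherence of 85% or higher". Three other places bear on how the 85% is counted.

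- Protocol deviations gives the measurement rule: "Protocol adherence will be assessed by comparing the response to the daily question about the performance of the intervention/exercise matches with the current period". The same section applies the minimum of 16 separately: below it, "PROs are documented, the participant will be excluded from the per-protocol analysis which will be performed as part of the sensitivity analyses".
- Missing Data says of the app data that "we will conduct complete-case analyses, assuming that the missing values are completely random". Participants who stop early contribute whatever they recorded.
- Analysis Principles for Final Analyses remarks that the intention-to-treat effect, defined as the effect of having the intervention available, mirrors the effect of the intervention itself "if there is high adherence to the pre-defined intervention schedule".

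No section states the denominator of the 85%, and none says whether one PRO is a day's entry or a single rating.

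**The concern.** A percentage threshold without a denominator is normally a real fault in a population definition. Here two candidates suggest themselves: days on which the daily question was answered, and all days on the schedule. The remark about adherence to the schedule can be read as favouring the second. A participant who logs 16 days of a 28-day trial, all matching, scores 16/16 = 100% on the first count and 16/28 = 57% on the second, and so moves from inside the set to outside it.

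If the rule were truly open, membership of a planned sensitivity analysis could be settled after the data had been seen. Under the SAP's assumption that values are missing completely at random, the choice would mainly change who is included and how precise the estimate is. If logging were related to stress, it could also move the estimate. The unit of a PRO adds a second question: with two primary outcomes rated daily, 16 PROs could in principle mean 16/2 = 8 days.

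**Working it through.** **Reading the text.** The measurement rule compares a response with the current period. An unanswered day offers no response to compare, and no sentence turns a missing answer into non-adherence. Days after a participant stops have no answers either, so on this reading they fall out without a further rule. The schedule remark belongs to the interpretation of the intention-to-treat effect; it mentions neither the per-protocol set nor a percentage. It says what behaviour is compared with, not which days are counted, and so fits either denominator.

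**What the minimum of 16 implies.** Let N be the scheduled days. On the scheduled reading, the matching days needed are ceil(0.85N):

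- N = 16: 14
- N = 17: 15
- N = 18: 16
- N = 20: 17
- N = 28: 24
- N = 42: 36

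From N = 18 upward, anyone who meets the 85% already has at least 16 logged days, so the separate minimum could exclude nobody. On the answered-day reading the minimum has a clear job: without it, one answered and matching day would score 100%. At 16 answered days the cut-off needs ceil(0.85 × 16) = 14 matches (87.5%).

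**How far the readings differ.** The SAP gives no figure to reproduce. Trial length and logging rate are assumptions here: N = 20, 28 or 42, and each day logged independently with probability q, the same for everyone. Suppose first that every logged day matches. With L ~ Bin(N, q), the share in the set is P(L ≥ 16) on answered days and P(L ≥ ceil(0.85N)) on scheduled days. The interval-width ratio (scheduled over answered) is the square root of the ratio of participants, or of the ratio of logged days; both are shown as a range.

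| N | q | Answered | Scheduled | Width ratio |
|---|---|---|---|---|
| 20 | 0.80 | 63% | 41% | 1.22–1.24 |
| 28 | 0.80 | 99.9% | 31% | 1.69–1.78 |
| 42 | 0.80 | 100% | 24% | 1.96–2.05 |
| 20 | 0.90 | 96% | 87% | 1.04–1.05 |
| 28 | 0.90 | 100% | 86% | 1.07–1.08 |
| 42 | 0.90 | 100% | 88% | 1.06–1.07 |
| 20 | 0.95 | 99.7% | 98.4% | 1.01 |
| 28 | 0.95 | 100% | 98.8% | 1.01 |
| 42 | 0.95 | 100% | 99.6% | 1.00 |

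For N = 16, 17 or 18 the two sets of fully matching participants coincide, because the minimum of 16 is then at least as strict as the 85%.

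**If some answers do not match.** Take N = 28 and a match probability of 0.95 per logged day. The answered-day share is the sum over L ≥ 16 of P(L) × P(Bin(L, 0.95) ≥ ceil(0.85L)); the scheduled-day share is P(Bin(28, 0.95q) ≥ 24). The results are 97% against 16% at q = 0.80, 97% against 62% at q = 0.90, and 98% against 87% at q = 0.95. The corresponding participant-based width ratios are √(0.970/0.163) = 2.44, √(0.972/0.617) = 1.26 and √(0.979/0.869) = 1.06.

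**The case for a change.** The strongest case for a change is that an analysis population should be stated, not inferred from the redundancy of another criterion. Counting an undocumented day as non-adherent is a defensible convention, and nothing in the SAP expressly rules it out. The per-protocol definition stands in this SAP and cites nothing else, so the gap cannot simply be assigned to the protocol. The answered-day reading also has a cost: 14 matches in 16 logged days qualifies, which is 14/28 = 50% of a 28-day schedule, 14/20 = 70% of a 20-day one and 14/42 = 33% of a 42-day one, and compliance on the unlogged days is never verified.

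Much of this stands as fact. The denominator is unstated, and at around 80% logging, or with imperfect matching, the two sets differ a great deal. What does not stand is the claim that the text supports both readings equally. The scheduled reading needs a rule for missing answers that the SAP does not contain, and it leaves the minimum of 16 idle in all but the shortest trials. The 8-day interpretation of a PRO requires counting two ratings from one day separately, which nothing in the SAP suggests. The cost in unverified days is a fair trade-off: the scheduled reading would instead treat a failure to log as a failure to adhere and would shrink the set.

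**Conclusion.** No change to the plan follows. This is a missing phrase that an analyst fills sensibly from the same section: adherence is the share of answered days on which the answer matches the period, and completeness is handled by the minimum of 16 daily entries. Followed that way, the additional per-protocol analysis is sound and consistent with the complete-case handling of the app data.

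The possible effect is not negligible everywhere. With full matching it is large at about 80% logging in trials of 20 days or more, small at 90%, and practically nil at 95%. With 95% matching over 28 days it is still noticeable at 90% logging. These figures rest on assumed trial lengths, assumed logging rates and a single logging probability for all participants, none of which the SAP supplies; logging that varies between people would change them. They measure the distance to a reading that the text does not favour, and they touch only a sensitivity analysis. A bias in the estimate, beyond a change in precision, would need logging to be related to stress, contrary to the SAP's working assumption. Writing the denominator down would record a definition already implied; it would not alter the analysis.
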